## 3.4 Placebo

Placebo capsules will be produced in collaboration with the laboratory at the department of Hepatology and Gastroenterology, AUH. The placebo capsules are produced from a suspension of 50% glycerol, 40% sterile saline and 10% food coloring in enterocapusles to make them indistinguishable from the FMT capsules. All capsules are kept at -80°C until use. Processing and handling follow standards of the tissue and cell legislation. The capsules have no taste, are odorless, and are stored in vials labelled "study capsules." The frozen FMT capsules and placebo capsules are identical in terms of visual appearance, weight, and vials and the final number of placebo capsules is varied between 10 and 30 to ensure blinding.

## 3.5 Randomisation

Randomisation will determine which group of patients will receive active treatment with FMT and which group will receive placebo capsules. Both participants and investigators will be blinded to the intervention.

Randomisation is performed by the project nurse at the Clinical Trial Unit at the department of Hepatology and Gastroenterology, AUH. The delivery is handled by the CEFTA laboratory staff after contact with the clinical staff. The randomisation list is established by the Clinical Trial Unit, Hepatology and Gastroenterology, AUH. Envelopes with procession information are packed according to the randomisation list. The CEFTA laboratory is continuously packing treatment boxes for each patient at randomisation according to the treatment with FMT + FMT or Placebo + FMT. The packaging of the boxes is standardised with double control and documented as a standard FMT for traceability as in routine FMT. The labeling on the packages does not reveal whether it contains placebo or FMT. Treatment boxes are marked with a number corresponding to the number drawn from the randomisation list, and at the start of the treatment it is ensured that these matches. The randomisation list is kept secret in the projects Trial Master File.

Premature unblinding is possible if investigators deem it necessary or in the event of conditions leading to interruption of the entire trial. This could be following several adverse events (AE) suspected to be in relation to active treatment with FMT, or if the trial terminates prematurely because of inability to include 20 patients. Any unblinding will follow the SOP "Kodebrud" and will be documented in the TMF.

## 3.6 Practical implementation and investigations

Twenty patients suffering from DM1 and severe GI neuropathy will be included in the study. The included patients will be identified during attendance in a specialised outpatient clinic in AUH to which they are referred to because of their GI symptoms. Prior to inclusion, standard clinical work-up including examination and blood samples have been performed to exclude competing diseases affecting the gastrointestinal system (celiac disease, thyroid disease, inflammatory bowel disease, infection and malabsorption). Colonoscopy will have been performed on clinical indication.

The trial will be performed at the Department of Hepatology and Gastroenterology at AUH. The participants remain outpatients and visit the department ten times. Investigations will be made at baseline and at the end of the two intervention periods.

# Table 1. Schedule of procedures

Week	-3	-2 (+1)	-2 (+1)	1	5 (+1)	5 (+1)	6 (+2)	10 (+2)
	Information and inclusion	Baseline investigations (I)	Baseline investigations (II)	1. Intervention	Investigations after 1. intervention (I)	Investigations after 1. intervention (II)	2. Intervention	Investigations after 2. intervention (I)
Visit No.	1	2	3	4	5	6	7	8
Inclusion								
Information	Х							
Informed consent	x							
In- and exclusion criteria	x							
Medical anamnesis	x							
Randomisation	x							
Exchanges								
Equipment handed out		x						
Intervention								
FMT or placebo				X				
FMT							Х	
Questionnaires								
Bowel diary	X			X			X	
GSRS-IBS		X			X			Х
PAGI-SYM		X			X			Х
IBS-IS		X			X			Х
COMPASS-31		X						
Measurements								
Wireless Motility capsule		X			X			Х
Low-dose CT			Х			X		
Breath test			Х			X		
Stool samples		X			X			Х
Blood samples		X			X			Х
Additional								
Adverse events					x			

#### **3.6.1** Information and inclusion (visit 1)

Potentially eligible patients are informed about the project and offered  $\geq$ 24h to consider participation. If the patients are willing to participate in the study, and they meet the in- and exclusion criteria, they will sign the ICF. If eligible, they will be assigned a unique study number and randomised to either active FMT or placebo. The patients will receive a bowel habit diary, a collection kit for faecal samples and a schedule for the study period.

#### 3.6.2 Baseline investigations I (visit 2)

The patients arrive at the department of Hepatology and Gastroenterology AUH following an overnight fast (at least six hours). If relevant, a pregnancy test will be performed. The patients will be served a standardised meal before initiating the investigation with the Wireless Motility Capsule. Furthermore, the patients will fill out the questionnaires and blood samples will be drawn. The patients will be advised to fill out the bowel habit diary for the following 7 days.

#### 3.6.2.1 Timeline visit 2

08.00-09.00	Questionnaires
09.00-09.30	Standardised meal and WMC ingestion
09.30-09.40	Blood samples

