## 2.4.2 Secondary endpoints

Patient-reported outcomes are obtained from the bowel habit diary. Each patient fills out the diary every day for one week at baseline, for one week starting at each day of the two interventions

and for one week at the follow-up at week 26. Bivariate comparions are made, comparing differences between FMT and placebo at a) Baseline vs first intervention, b) Baseline vs second intervention, c) Baseline vs longterm follow-up (week 26) for the following variables:

- 1. Median stool consistency (Bristol scale)
- 2. Number of passages of hard stools (BS 1-2)
- 3. Number of passages of liquid stools (BS 6-7)
- 4. Median number of bowel openings per 24 hours
- 5. Number of nightly bowel openings (from bedtime until morning)
- 6. Number of episodes with involuntary defaecation
- 7. Glycemic control measured by patient reported use of insulin (IE)

Patient-reported measures from the schedule of side effects and telephone call 1 week after each intervention

- 8. Mild adverse events (grade 1) following FMT or placebo assessed by CTCAE v5.0
- 9. Adverse events in week 5-8
- 10. Serious adverse events during longterm follow-up

Patient-reported outcomes from questionnaires completed at baseline and 4 weeks after each intervention period and at 26 weeks follow-up. Bivariate comparisons baseline vs week 4, baseline vs week 8, baseline vs week 26:

- 11. Change in Gastrointestinal syndrome rating scale irritable bowel version questionnaire (GSRS-IBS)
- 12. Change in patient assessment of upper gastrointestinal symptom severity index (PAGI-SYM)
- 13. Change in irritable bowel syndrome impact scale (IBS-IS)

Objective measures from the wireless motility capsule performed at baseline and 4 weeks after each intervention period:

- 14. Transit time through the small intestine
- 15. Colonic transit time
- 16. pH drop from the small intestine to the colon

Objective measures from the low-dose CT scan performed at baseline and 4 weeks after the first intervention period:

- 17. Volume of the a) small intestine and b) the colon
- 18. Volume of gas in a) the small intestine and b) the colon

Objective measures from the breath test performed at baseline and 4 weeks after the first intervention period:

19. Rise in hydrogen PPM measured in breath test for small intestinal bacterial overgrowth

Microbiota analysis on faecal samples collected at baseline and 4 weeks after each intervention period:

20. Alpha-diversity of faecal microbiota, 16S

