#### 3.6.3 Baseline investigations II (visit 3)

The patients will arrive in the morning at the Department of Radiology at AUH for the second day of baseline investigations. They will arrive fasting (for at least six hours). The patients will undergo a low-dose high-resolution CT scan. The investigation takes approximately 30 minutes.

Afterwards the patients will go to the department of Hepatology and Gastroenterology to the investigation room at the second floor. The patients will undergo a breath test. Glucose is given orally and the patients will breathe into a breathalyser and the amount of methane and hydrogen in the exhaled air will be measured. The investigation takes approximately two hours.

#### 3.6.3.1 Timeline visit 3

08.00-08.30 Low-dose CT scan 09.00-11.00 Breath test

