#### 6.1.1.3 Wireless Motility Capsule

The WMC is an orally ingested data recording device that enables simultaneous assessment of regional and whole gut transit. The WMC is CE marked and approved by the US Food and Drug Administration for evaluation of patients with suspected delayed gastric emptying and evaluation of colonic transit time in patients with chronic constipation. The WMC is contraindicated to patients with a history of gastric bezoar, swallowing disorders, dysphagia to food or pills, suspected

stricture or fistulae along the GI tract, physiological GI obstruction, GI surgery within the previous 3 months, Crohn's disease, diverticulitis or an implanted or portal electromechanical medical device(31).

The most serious AEs associated with the WMC are the inability to confirm passage of the capsule outside the body, capsule retention and obstruction. In a previous trial with nearly 6000 patients receiving WMC there were 20 reports of prolonged capsule retention (5 in the stomach, 2 in the small intestine and 13 in the colon) which yield a retention rate of 0,33%(30). An upper endoscopy was required for extraction of the 5 capsules that were retained in the stomach. Of the remaining 15 cases, only 1 capsule required drug intervention. The other 14 capsules passed spontaneously. None of the patients required surgical intervention. If it cannot be confirmed that the capsule has passed five days after ingestion the manufacturer's follow-up recommendations should be followed. This is based on the location of the capsule which is determined by the pH profile obtained during the study. If the pH profile suggests that the capsule is retained in the stomach or bowel. Due to the low risk of obstruction once the capsule is in the colon, no specific follow-up is necessary if the capsule is retained in this area.

Other side effects associated with WMC include abdominal pain, dysphagia, nausea and diarrhea. However, as many of the patients had these symptoms at baseline, these side effects have been difficult to determine if they were caused by the WMC. Patients are provided information about the risks in the participants information sheet, which they are urged to read comprehensively prior to consenting to participate.

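### Section 3.6.2 and Table 1 place the baseline bowel diary in different weeks, and the 3.6.2 week follows the capsule visit, so the reference for endpoints 1-7 may be disturbed

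*Protocol*

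**What the plan says.** Section 2.4.2 bases endpoints 1-7 on daily diary entries: "Each patient fills out the diary every day for one week at baseline, for one week starting at each day of the two interventions". A further diary week is kept at week 26. The analysis is described as "comparing differences between FMT and placebo at a) Baseline vs first intervention", then likewise for the second intervention and week 26. One baseline week therefore serves seven endpoints at three time points.

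Three places bear on when that week falls:

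- Section 3.6.1, visit 1: "The patients will receive a bowel habit diary, a collection kit for faecal samples and a schedule for the study period".
- Table 1 marks the bowel diary under visits 1 (week -3), 4 and 7. It has no diary mark under visit 2.
- Section 3.6.2, visit 2: "The patients will be advised to fill out the bowel habit diary for the following 7 days".

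Visit 2 follows an overnight fast. Section 3.6.2 adds: "The patients will be served a standardised meal before initiating the investigation with the Wireless Motility Capsule". Visit 3 (section 3.6.3) brings a further fast, the CT scan and the breath test, for which section 3.3.4 gives 80 g of glucose. Table 1 puts visits 2 and 3 in the same window, week -2 (+1). Section 3.3.7 provides for supplemental insulin on fasting days, whether for investigations or for dosing.

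On the capsule, section 6.1.1.3 states: "Other side effects associated with WMC include abdominal pain, dysphagia, nausea and diarrhea". It goes on to say that attribution is difficult because many patients already had such symptoms. Section 6.0 expects no adverse events from the capsule.

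**The concern.** A baseline diary should describe the patient's usual bowel function and insulin use. Under section 3.6.2 it is instead kept in the days after a fast, a test meal and an ingested capsule, and possibly across a second fast with a large glucose load. The diary weeks at visits 4 and 7 schedule no new capsule study, CT or glucose load, and no investigation is scheduled at week 26. Baseline and later weeks are then disturbed in different ways.

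The conflict with Table 1 also means that staff could follow either instruction. Patients could then have baseline weeks recorded under different conditions, with nothing in the protocol to show which applied. That would affect the pilot estimates of change in stool counts, night-time openings, involuntary defaecation and insulin use.

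**Working it through.** The protocol states no figure here that could be reproduced. The check sets the timing statements side by side and then illustrates what a disturbed baseline would do.

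**Timing**

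| Source | Baseline diary week | Relation to investigations |
|---|---|---|
| Table 1, with hand-out in 3.6.1 | From visit 1, week -3 | Can precede all of them |
| Section 3.6.2 | 7 days following visit 2, week -2 (+1) | Follows capsule ingestion; may contain visit 3 |

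The diary marks at visits 4 and 7 sit at the visits where those diary weeks start. That supports reading the visit 1 mark as the start of the baseline week, although it could merely record the hand-out.

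Whether visit 3 falls in the 3.6.2 week is not fixed. If (+1) means one extra week, each visit can fall in a 14-day window, so the two can be 0 to 13 days apart when visit 2 comes first. Visit 3 lies in the diary week if the gap is at most 7 days, and outside it otherwise.

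**Effect on the endpoints**

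Let k be the number of disturbed baseline days and x the mean change in bowel openings on each such day, the same in both arms, with no treatment effect.

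- False within-arm change in the weekly count = -k × x.
- False between-arm difference = (-k × x) - (-k × x) = 0.

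The protocol gives neither k nor x, so both are assumptions. A simulation used 20,000 runs, 10 patients per arm (Figure 1), an assumed mean of 3 openings per day, Poisson counts and gamma variation between patients. Within-arm results:

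| k | x | Weekly count | Daily median |
|---|---|---|---|
| 0 | - | about 0 | about 0 |
| 1 | +1 | -1.0 | -0.12 |
| 2 | +1 | -2.0 | -0.26 |
| 3 | +1 | -3.0 | -0.40 |
| 2 | +2 | -4.0 | -0.46 |
| 2 | -1 | +2.0 | +0.30 |

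The expected between-arm difference is zero by construction. The largest simulated value in any scenario run (k up to 5) was 0.07 openings per week, against standard deviations of 2.9 to 3.9. With k = 2 and x = +2, the standard deviation of the between-arm difference rose from 2.9 to 3.2.

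**Counts against medians.** A total takes in a disturbed day in full; a median takes it in only partly when the shift is large. For k = 2 and x = +2 the mean per day moves by 4/7 = 0.57 and the median by 0.46. The protection is modest: for k = 2 and x = +1 the figures are 2/7 = 0.29 and 0.26, and for x = -1 they are 0.29 and 0.30. Counts (endpoints 2, 3, 5, 6) and insulin use (endpoint 7) are thus the more exposed, mainly to large disturbances. Insulin has the most direct route, since supplemental doses may be given on test days and visit 3 adds a glucose load.

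**The case against.** The planned comparison is largely protected. The baseline investigations precede treatment and are the same in both arms, so a common shift drops out of FMT versus placebo. It also drops out when a patient's first and second intervention weeks are compared, because both use the same baseline. This stands, and it limits the point to noise and within-arm change.

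The dosing weeks are not clean either. They start with a fast, metoclopramide and a large number of capsules, and the supplemental insulin scheme covers dosing days too. A motility capsule swallowed at visit 5 (week 5 (+1)) could still be in transit at visit 7. This also stands: an undisturbed baseline does not make the weeks fully alike. It does remove a disturbance that is avoidable and differs from the one in the dosing weeks.

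A reader might infer three stronger things that the document does not support:

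- That the baseline will look falsely bad. Fasting could reduce stools, section 6.1.1.3 calls attribution to the capsule difficult, and section 6.0 anticipates no capsule adverse events.
- That 2 of 7 baseline days are fasting test days, against 1 of 7 after dosing. This needs visit 3 to fall in the week and visit 2 to count as a diary day. If the 7 days start the day after visit 2, at most 1 of 7 is a fasting test day.
- That the pilot estimate is biased in favour of treatment. The sign is unknown, the between-arm estimate is not shifted, and no section names within-arm change as the design input for the next trial.

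If Table 1 governs and the diary is completed before visit 2, the disturbance does not arise and only the contradiction remains.

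**Conclusion.** The point holds in limited form. Section 3.6.2 and Table 1 conflict on the reference week for endpoints 1-7, and this needs no assumption about effect size beyond reading the Table 1 mark as the diary week.

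Under section 3.6.2 the week may also be disturbed by the investigations, in an unknown direction and amount. The illustrative within-arm error is k × x openings per week in size: 1 to 3 for one to three days shifted by one opening, with either sign. These values rest on assumed inputs and are not estimates for this trial.

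The FMT versus placebo comparison suffers mainly added noise. The exposure that matters is within-arm change from baseline, above all after visit 7. From then on the arms contrast two doses of FMT with placebo followed by FMT, so any overall reading of FMT rests on change from this baseline. The weakness does not undermine the trial, but it should be corrected because correction is easy.

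**What to change.** Reconcile section 3.6.2 with Table 1. State in both that the 7-day baseline diary is completed between visit 1 and visit 2, before any fast, capsule, CT or glucose load, and is returned at visit 2. Replace the sentence in 3.6.2 that starts the diary after visit 2, and let the Table 1 entry show completion rather than hand-out alone.

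This uses a diary already supplied at visit 1 and the nominal week between weeks -3 and -2. It also lines the diary up with the GSRS-IBS, which covers the previous week (section 3.3.1) and is filled in at visit 2 before the capsule is swallowed (section 3.6.2.1).

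The cost is one sentence, one table entry and a requirement that visit 2 be at least 7 days after visit 1.

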#### 3.6.3 Baseline investigations II (visit 3)

The patients will arrive in the morning at the Department of Radiology at AUH for the second day of baseline investigations. They will arrive fasting (for at least six hours). The patients will undergo a low-dose high-resolution CT scan. The investigation takes approximately 30 minutes.

Afterwards the patients will go to the department of Hepatology and Gastroenterology to the investigation room at the second floor. The patients will undergo a breath test. Glucose is given orally and the patients will breathe into a breathalyser and the amount of methane and hydrogen in the exhaled air will be measured. The investigation takes approximately two hours.

#### 3.6.3.1 Timeline visit 3

08.00-08.30 Low-dose CT scan 09.00-11.00 Breath test

#### 3.6.4 1. Intervention. FMT or Placebo (visit 4)

The patients will receive treatment with either active FMT or placebo. The capsules will be administered by a nurse not otherwise involved in the study. The patients will continue their usual daily living while keeping a bowel diary for 7 days. They will furthermore be advised to fill out a daily report on side effects for 7 days. After 1 week, a telephone call will be made to ensure that no major side effects have occurred.

#### 3.6.5 Investigations after 1. Intervention I and II (visit 5 and 6)

After 4 weeks since the first intervention, the investigations made at baseline will be repeated.

## 3.6.6 2. Intervention. FMT (visit 7)

During the second intervention period all patients will receive the active treatment with FMT. The following 4 weeks the patients will continue normal daily activities. They will be advised to fill out the diary and the report on side effect for 7 days following the FMT. A telephone call will be made after 1 week to follow-up on potential side-effects.

## 3.6.7 Investigations after 2. Intervention I (visit 8)

After an additional 4 weeks since the second intervention, investigations will be repeated once again except for the breath test and low-dose CT scan.

## 3.6.8 Follow-up post study

The patients will be offered further treatment with FMT (open label), if they have reported effect of the treatment, and they experience relapse of gastrointestinal symptoms. After completing the study period, the patients will be contacted every two months by telephone to follow up on their gastrointestinal symptoms. If the patients report relapse of symptoms, they will be asked to complete the GSRS-IBS questionnaire. If they achieve 40 point or above in the questionnaire, the patients will be offered treatment with FMT. The patients will also be asked to collect stool samples for microbiome analysis. FMT treatment may be repeated at later recurrence of symptoms, in the following two years, after the patients have completed the study. The follow-up post study is an additional option for the patients. They may at any time refuse to be contacted or to receive further treatment.

# 4.0 Statistical considerations

## 4.1 Sample size

This is the first study with FMT to patients with DM1 and therefore the assumptions for formal power calculations are not present. We expect that a group of n = 20 patients with DM1 is sufficient to determine whether there are any serious side effects associated to administration of FMT.

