# 2.3 Hypotheses

## 2.3.1 Primary H0

1. Oral intake of FMT capsules is safe and well tolerated in patients with DM1, including those with prolonged gastric emptying and small intestinal transit.

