## 2.3.2 Secondary H0

2. Oral intake of FMT changes the microbiota of the colon and the effect lasts for at least 4 weeks.

3. Oral intake of FMT is superior to placebo in reducing gastrointestinal symptoms in patients with DM1.

4. The effect of two doses of oral intake of FMT (separated by 4 weeks) is superior to one dose.

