# 2.4 Endpoints

## 2.4.1 Primary endpoint

Number of adverse events of severity grade 2 or more assessed by CTCAE v5.0 during the first week after first intervention (FMT or placebo).

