# 6.0 Risks, adverse events, and nuisance

We expect no long-term risks following participation. Side effects of FMT tend to be mild and short-lasting. Treatment with FMT is generally well tolerated, but specific side effects are sparsely elucidated. Experience has shown that about one-third of patients receiving FMT experience transient diarrhea, nausea or bloating(16, 33, 34). Less than 1 in 10 experience fever and discomfort in the hours after FMT. For most patients, the condition lasts less than a day and does not require treatment. The patient is carefully instructed after each treatment and receives information of how to contact the department in case of worsening or side effects. Approximately 1 in 20 develops symptoms compatible with bacterial overgrowth. These are treated according to local instructions of the department. Less than 1% of the patients receiving FMT experience severe long-term symptoms of infection with infectious disease from the donor. The risk is reduced as much as possible by thorough selection and screening of donors and donor faeces on accordance with tissue standards and the European Union Tissue and Cells Directives which leads to the safety standards comparable to handling of blood components. The application form of capsule FMT is minimally invasive. The inconvenience is ingestion of the many capsules and overnight fasting prior to ingestion of the capsules. Treatment with peristalsis-promoting medication helps in addition to accelerated emptying of the stomach for possible nausea.

Blood sampling may be associated with minor discomfort, bleeding, hematoma, and/or bruising, and there is a minimal risk of infection or inflammation, however this is easily treated. There are no known risks involved with faecal sampling.

The wireless Motility Capsule is a noninvasive and painless method of obtaining important data of the GI tract. We anticipate no adverse events (AE) caused by the Wireless Motility Capsule, however, there is a low risk of retention of the capsule. If a patient does not pass the capsule within 4 weeks, they will be offered an abdominal x-ray and possibly gastroscopic, colonoscopic or surgical removal of the capsule.

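### Section 4.1 credits 20 patients with a safety finding they cannot deliver for uncommon serious harms, and the hypotheses headed H0 state the hoped-for conclusions

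*Protocol*

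**What the plan says.** Protocol section 4.1 first says that "the assumptions for formal power calculations are not present", because FMT has not been studied in this population before. It then gives the expectation that "n = 20 patients with DM1 is sufficient to determine whether there are any serious side effects associated to administration of FMT". No other reason for the number is offered.

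Section 2.3.1, headed Primary H0, reads "Oral intake of FMT capsules is safe and well tolerated in patients with DM1" and extends this to patients with slow gastric emptying or small bowel transit. Section 2.3.2, headed Secondary H0, lists three further statements in the same direction, among them "Oral intake of FMT is superior to placebo in reducing gastrointestinal symptoms in patients with DM1".

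The primary endpoint (2.4.1) is the number of CTCAE v5.0 adverse events of grade 2 or higher in the week after the first FMT or placebo dose. Section 3.1 gives FMT to every patient in the second four weeks. On background rates, section 6.0 says "Less than 1% of the patients receiving FMT experience severe long-term symptoms of infection" transmitted from the donor. Section 4.2 reports adverse events descriptively and leaves detail to the statistical analysis plan.

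**The concern.** A sample-size statement tells the reader what the trial will be able to say. This one promises an answer on whether any serious side effects exist. A sample of 20 cannot give that answer unless the harm is common.

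This matters because safety is the primary purpose. Section 2.6.4 argues that large trials would be unethical until safety and tolerability have been secured in a small group. If no serious event is seen, section 4.1 as worded invites the report that there are none. What the data would then support is a fairly high upper limit on the rate.

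The H0 headings point the same way. A null hypothesis is what stands when the data are too few to contradict it. With safety as the null, a small and uninformative trial favours the desired conclusion by default. With superiority as the null, the efficacy hypotheses are reversed too.

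**Working it through.** **The protocol's own figure.** N = 20 cannot be reproduced. Section 4.1 gives no significance level, power, event rate or margin. The check is therefore of what 20 patients can show.

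**Inputs**
- Patients exposed to FMT by the end of the second period: 20 (sections 3.1 and 3.6).
- Patients on FMT in the primary endpoint window: about 10. Figure 1 shows 10 and 10. The body text states no allocation ratio, so 1:1 is assumed.
- Rate of severe donor-derived infection: below 1% (section 6.0). The value 1% is used, which favours the protocol's claim.

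**Chance of seeing at least one case,** 1 − (1 − p)^n

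| True rate p | n = 20 | n = 10 |
|---|---|---|
| 1% | 1 − 0.99^20 = 18.2% | 1 − 0.99^10 = 9.6% |
| 10% | 1 − 0.90^20 = 87.8% | 1 − 0.90^10 = 65.1% |
| 15% | 1 − 0.85^20 = 96.1% | 1 − 0.85^10 = 80.3% |

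The 10% and 15% rows are assumed rates, shown for range. At 1%, a trial of 20 shows no case about 82% of the time. Even if all 40 patients allowed under section 5.4 were exposed, the chance at 1% would be 1 − 0.99^40 = 33.1%.

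**Number needed for a 95% chance of at least one case at 1%:** ln 0.05 / ln 0.99 = 298.1, so 299 patients.

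**Rate at which 20 patients would be enough.** Solving 1 − (1 − p)^20 = 0.95 gives p = 13.9%. For an 80% chance it gives p = 7.7%.

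**Upper limit on the true rate when no event is seen**
- 0/20, one-sided 95%: 1 − 0.05^(1/20) = 13.9%. Two-sided 95%: 1 − 0.025^(1/20) = 16.8%.
- 0/10, one-sided 95%: 1 − 0.05^(1/10) = 25.9%. Two-sided 95%: 1 − 0.025^(1/10) = 30.8%.

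The n = 20 results test the sentence in 4.1, which concerns serious side effects in everyone given FMT. The n = 10 results describe the controlled first period, where the primary endpoint is measured and which 4.1 does not mention. They apply to the proportion of patients with an event, whereas the endpoint in 2.4.1 counts events.

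**Direction of the hypotheses.** The four statements under the H0 headings are that FMT is safe and tolerated, that it changes the microbiota, that it beats placebo, and that two doses beat one. Each is what the investigators hope to show. None is a statement of no effect or of unacceptable harm.

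**The case against.** The best defence is that this is openly a pilot, that 4.1 states an expectation and has just disclaimed a power calculation, and that the harms of real interest are those peculiar to diabetic neuropathy, whose rate is unknown. Part of this stands. The number 20 is not at fault, and for frequent serious harm it is informative, as the 10% and 15% rows show. But the sentence speaks of any serious side effects, and the protocol itself names a serious harm far rarer than 20 patients can reveal.

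It may also be said that all 20 patients eventually receive FMT, so the 10-patient limits do not bear on 4.1. That is right for the sentence itself. They bear on the primary endpoint, for which the protocol gives no size rationale at all.

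A reader might go further and infer that the trial will declare FMT safe from a non-significant comparison. The documents do not support that. The protocol names no test and no decision rule for safety, its safety reporting is descriptive, and superiority claims under the same kind of heading suggest mislabelling. Fisher's exact test at a two-sided 5% level would need 5/10 against 0/10 to reject, but the test and level are assumptions, so this shows scale only.

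A reader might also take "Approximately 1 in 20 develops symptoms compatible with bacterial overgrowth" as a second serious-event rate. Section 6.0 does not call that event serious, so it is not used here.

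**Conclusion.** The concern holds as a fault of wording in 4.1 and in the hypothesis headings. It should be fixed, but it does not undermine the design. The claim in 4.1 fails for uncommon serious harms: the chance of seeing a 1% harm in 20 exposed patients falls far short of determining whether it exists, and a clean result would still leave a true rate of roughly one in seven unexcluded. In the controlled window, a clean result in the FMT arm would leave roughly one in four unexcluded.

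These conclusions rest on independent patients, exact binomial limits, equal allocation, 20 patients actually exposed, and 1% as the upper end of the protocol's own statement. A lower true rate makes the case stronger.

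The inverted hypotheses are an error in the text as it stands, whether of label or of intent. Their effect on the trial's conclusion depends on a decision rule that the protocol does not state. A later analysis plan can add detail but cannot make these sentences true.

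**What to change.** **Section 4.1.** Replace the claim of sufficiency with text to this effect: the sample of 20 is a pilot size with no formal power basis; no serious event among 20 patients given FMT would exclude a true rate above about 14%, and none among the 10 in the concurrent FMT arm a rate above about 26% (one-sided 95%); rarer serious harms cannot be excluded.

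**Section 2.3.1.** Restate as an estimation objective: the proportion of patients with at least one grade 2 or higher event in each arm in the primary window, and the difference between arms, with 95% confidence intervals.

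**Section 2.3.2.** State the nulls of hypotheses 2 to 4 as no change or no difference, and keep the present statements as the alternatives.

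**Interpretation.** Add that safety will not be concluded from a non-significant comparison.

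**Cost.** Wording only. Sample size, allocation, endpoints, visits and treatment stay as they are. The price is a more modest claim about safety.
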